2.1 PRIMARY OBJECTIVE

AIM: To assess the safety and efficacy of subcutaneous abatacept in an open-label trial of refractory JDM in 10 adults and children.

- **Hypothesis A: *Abatacept will be well-tolerated and safe in treatment–refractory JDM patients.*** For this, the NCI Common Terminology criteria version 4.0 June 2010 will be applied. Medical records will be reviewed for the 6 months prior to enrollment to obtain adverse events prior to beginning abatacept, which will be compared to any adverse events that develop after abatacept was initiated. Particular attention will be given to serious adverse events and infections. Patient evaluations will include: vital sign measurement, physical examination, and laboratory parameters for hematology and routine chemistries.
- **Hypothesis B: *Patients will clinically improve after treatment with abatacept.*** We hypothesize that at least 6 of 10 patients will meet the myositis preliminary definition of improvement after receiving 24 weeks of therapy with abatacept.

Definitions of improvement (DOIs) for clinical trials in IIM have recently been proposed by the IMACS Group (International Myositis Assessment and Clinical Studies) for adult and pediatric myositis utilizing six core set measures among five domains of myositis disease activity (38) (**see Appendix C**). They are:

- a) Physician global disease activity;
- b) Parent/patient global disease activity;
- c) Muscle strength, utilizing manual muscle strength testing (MMT8);
- d) Physical function assessment using the (Childhood) Health Assessment Questionnaire (CHAQ);
- e) Laboratory assessment using the most abnormal serum muscle enzyme level; and
- f) Extra-muscular disease activity using the Myositis Disease Activity Assessment Tool (MDAAT). (see section 14.0: assessment tools: description) (39)

For this clinical trial, the primary endpoint will be the published Definition of Improvement (DOI): 3 of any of the 6 core set measures improved by $\geq 20\%$, with no more than 2 of the core set measures worsening by $\geq 25\%$ (worsening measures cannot include the muscle strength). (Appendix D1) (38)

The PRINTO Group (Pediatric Rheumatology International Trials Organization) has developed and validated a core set of outcome variables for the evaluation of response to therapy in JDM. (40) (Appendix C)

The additional PRINTO core set activity measures are:

- 1) Childhood Myositis Assessment Scale is used as a measure of strength;

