3.1 ENDPOINTS

Primary

The *primary endpoint* of this trial is to establish safety and efficacy of Abatacept in patients with refractory Juvenile Dermatomyositis

- a) Safety: Abatacept will be well-tolerated and safe.
- b) Improvement in myositis disease activity: the published IMACS myositis definition of improvement will be achieved in at least 6 of 10 patients at the end of the trial (38).

Secondary

- a) To evaluate the response rate to Abatacept in JDM using the PRINTO definition of improvement, including criteria for minimal, moderate and major clinical response (40, 41).
- b) To evaluate the response rate to Abatacept using newly developed criteria for myositis clinical response, which are pending ACR-EULAR approval (Appendix D2), as well as other top performing criteria considered at the International Myositis Response Criteria Consensus Conference.
- c) To examine response to treatment in individual core set measures of disease activity as developed by IMACS, including physician and patient/parent global activity, muscle strength (by manual muscle testing), physical function (by HAQ/CHAQ), muscle enzymes, and extra-muscular activity (by the Myositis Disease Activity Assessment Tool)

- d) To examine other core set activity measures as developed by PRINTO, including the Childhood Myositis Assessment Scale, the Disease Activity Score and CHQ-PF50
- e) Steroid-sparing benefit: 20% reduction of the corticosteroid therapy will be achieved in 6 of 10 patients at the end of the trial
- f) To examine improvement in patient reported outcomes, including health-related quality of life and fatigue measures, including the PROMIS and PedsQL fatigue questionnaires. Both patient and parent questionnaires will be obtained, for patients < 18 years of age.
- g) To examine improvement in cutaneous activity, using the Cutaneous Dermatomyositis Area and Severity Index (CDASI) and the Dermatology Life Quality Index, as well as periungual nail fold capillary density. To document changes in cutaneous findings by standardized photography.
- h) To examine improvement in muscle inflammation by examining a thigh/pelvis STIR MRI at baseline and 6 month follow-up. MRI readings will be blinded to the clinical assessment information, including, if possible, date of assessment, and study drug dose.
- i) To examine that disease damage does not increase while under treatment with abatacept, by examining the Myositis Damage Index at baseline and 6 month follow-up.

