4.0 SUBJECT POPULATION

Enrolled patients will include male and female, adults with a definite or probable diagnosis of JDM and pediatric patients \geq seven years of age and older with definite or probable JDM (using the criteria of Bohan and Peter-Appendix A) [33] with greater than four months of disease duration. Patient body weight will be at least 25 kg. Patient enrolment will occur at the GWU Myositis Center of the Medical Faculty Associates. The total number of subjects will be 10. A diagnosis of DM prior to age 18 is considered JDM; patients with JDM enrolled after age 18 will continue to be classified as JDM.

A log will be kept of all patients screened for study enrollment and will document the reasons for exclusion for each subject not entered. Every effort will be made to keep patients in the study until they complete all study procedures. We plan to screen up to 30 patients in clinic to enroll 10 patients. Additional patients may be screened by phone and not seen in clinic if not qualified for the protocol.

4.1 Inclusion Criteria:

In order to qualify for participation, a subject must meet all of the following criteria:

1	Considering 1A-1F below, does the subject have documented criteria for probable (2 + rash) or definite (3-4 + rash) juvenile DM by the criteria of Bohan and Peter?
	
 a. Does the subject have documented symmetric proximal muscle weakness on exam? b. Does the subject have documented Gottron's papules or Heliotrope rash on exam? c. Does the subject have documented elevations of any of the following muscle enzymes (CK, LD, AST, ALT or aldolase)? d. Was the age at diagnosis < 18 years? e. Has the subject had an EMG and if so, if so, does the subject have documented EMG evidence for myopathy f. Does the subject have documented muscle biopsy evidence of dermatomyositis?
2	Is the body weight at least 25 kg or over?
3	Is the subject at least 7 years or older?
4	Does the patient reside within the United States or Canada?
5	Considering 5A-5J below, Does the patient have refractory myositis? (As defined by the intolerance to or an inadequate response to corticosteroids plus at least one other IS agent?)
	a. Has the patient had intolerance or an inadequate response to prednisone for at least one month?
	b. Has the patient had intolerance at any time, or an inadequate response for at least 3 months to azathioprine at least 2 mg/kg/d or 150 mg/day?

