15.0 STATISTICS/DATA ANALYSIS

Statistical Plan:

This is an open label nonrandomized trial to assess the safety and efficacy of subcutaneous abatacept in 10 patients (children and adults) with juvenile onset refractory dermatomyositis (JDM).

We postulate that at least 6 of 10 patients with JDM will meet the myositis preliminary definition of improvement (DOI) after receiving 24 weeks of therapy with abatacept. Data will be entered and stored in the RedCap database, licensed to George Washington University. Primary analyses will be performed using intention to treat regardless of compliance with therapy or trial protocol. We will also perform analyses that include only those participants with known outcome data.

Summary statistics will be generated to describe the study samples. Descriptive statistics, including measures of central tendency (e.g. means, medians) and estimates of spread (e.g. standard deviations) will be used for continuous variables, including reporting of adverse event frequencies, core set measure assessments, and demographic and clinical variables. Non-parametric Wilcoxon signed rank tests will be used to investigate changes in continuous variables. 95% confidence intervals will be calculated for all point estimates.

We will examine the percentage of subjects meeting the DOI (20%), as well as moderate (DOI 50%) or major improvement criteria (DOI 70%), as well as frequency of patients achieving clinically inactive disease.

Due to the small number of subjects, it is unlikely that any statistical test would have the power to detect significant differences in any of the measured variables. We will therefore look not only at the percentage of subjects meeting improvement criteria by the DOIs, but also look for an improvement in individual core set myositis disease activity measurements of muscular and extra-muscular disease activity, as well as the in the patient-reported outcome measures, cutaneous assessments and MRI. We will also examine responsiveness after treatment using standardized response means and correlation degree of change between the measures. Differences between initial

and 24 weeks values will be analyzed by Student t distribution and Wilcoxon matched pair tests.

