Statistical analyses will be performed by using GraphPad InStat version 3.00 for Windows 95 (GraphPad, San Diego, CA) and/or SAS System for Windows, version 9.1.3 (SAS Institute, Cary, NC). For all statistical tests, a P-value of < 0.05 will be utilized to indicate statistical significance.

Results of this project may lead to the development of larger study that will have the statistical power to detect significant differences in the measured variables after treatment of JDM with abatacept.

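### Section 15 classes adverse event frequencies as continuous and names no interval method for binary or count safety outcomes, although safety is co-primary and n = 10

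*Combined protocol and SAP*

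**What the plan says.** Section 3.1 makes safety part (a) of the primary endpoint: "Safety: Abatacept will be well-tolerated and safe". It gives no numerical criterion. Section 2.1, Hypothesis A, adds that "Particular attention will be given to serious adverse events and infections". It also says that adverse events will be collected from records for the six months before enrolment, "which will be compared to any adverse events that develop after abatacept was initiated", but ties no method to that comparison.

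Section 4.0 fixes the size: "The total number of subjects will be 10".

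On analysis, Section 15 says that measures such as means, medians and standard deviations "will be used for continuous variables, including reporting of adverse event frequencies", and the same sentence goes on to list core set measures, and demographic and clinical variables. It then states: "95% confidence intervals will be calculated for all point estimates". The synopsis repeats both statements. The t distribution appears once in Section 15, for differences between initial and week 24 values. Section 15 has a separate sentence on the percentage of subjects meeting the improvement criteria, but no matching sentence for patients with an adverse event. Sections 3.2, 11 and 12 cover how safety data are collected and reported, not how they are analysed.

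**The concern.** Serious adverse events and infections in ten patients are either yes/no outcomes per patient or small counts. Mean and SD are poor tools for them, and an interval built from mean and SD breaks down when events are rare. With no event the SD is zero and the interval has no width. With one or two events its lower limit is below zero.

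No event, or one, is a plausible result in a trial this small. It is also the result most easily read as reassurance. If a co-primary safety finding were printed as 0 (SD 0) with limits 0 to 0, a reader would not see that a true rate near 30% has not been excluded.

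The plan also does not say what an adverse event frequency is. It could be the share of patients with at least one event, or the number of events per patient. The two need different intervals.

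**Working it through.** The documents give no adverse event rate, safety interval or safety threshold for this trial, so there is no planned figure to reproduce. The check asks what different interval methods return at n = 10.

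**Inputs.** n = 10 (Section 4.0); 95% level (Section 15), taken as two-sided because the plan does not say. The numbers of patients with an event, x = 0, 1, 2, are hypothetical.

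**Mean and SD treatment.** Score each patient 0 or 1. The mean is p = x/10, SD = sqrt(10·p·(1−p)/9), and the interval is p ± t(0.975; 9 df) × SD/sqrt(10), with t = 2.262.

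- x = 0: SD = 0, so 0 ± 0. The Wald interval is also 0 to 0.
- x = 1: SD = sqrt(0.9/9) = 0.316; SE = 0.100; 0.10 ± 0.226.
- x = 2: SD = sqrt(1.6/9) = 0.422; SE = 0.133; 0.20 ± 0.302.

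**Exact (Clopper-Pearson).** The lower limit is the 0.025 quantile of Beta(x, 11−x) and the upper limit the 0.975 quantile of Beta(x+1, 10−x). At x = 0 the lower limit is 0 and the upper limit is 1 − 0.025^(1/10) = 0.308. At x = 1 the lower limit is 1 − 0.975^(1/10) = 0.0025.

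| Patients with an event | t interval | Exact interval |
|---|---|---|
| 0 of 10 | 0 to 0 | 0 to 30.8% |
| 1 of 10 | −12.6% to 32.6% | 0.25% to 44.5% |
| 2 of 10 | −10.2% to 50.2% | 2.5% to 55.6% |

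At 0 of 10, other sound choices agree with the exact interval in substance: the Wilson interval is 0 to 27.8%, and the one-sided 95% exact upper bound is 1 − 0.05^(1/10) = 25.9%.

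**How likely is 0 of 10?** The chance is (1 − p)^10. Section 1.3.2 reports 6 serious events among 190 juvenile idiopathic arthritis patients in four months (6/190 = 3.2% of patients at most) and serious infections in 3.0% of adult rheumatoid arthritis patients on abatacept. Neither population is refractory juvenile dermatomyositis over 24 weeks, so a range is assumed.

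| True rate | Chance of 0 of 10 | Coverage of nominal 95% t interval |
|---|---|---|
| 3% | 74% | 26% |
| 10% | 35% | 65% |
| 20% | 11% | 89% |

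Coverage was enumerated over the binomial distribution. Almost all of the shortfall is the zero-event case: at 3%, 1 − 0.737 = 0.263, and the computed coverage is 0.262. The exact interval covers at least 98.7% at each of these rates.

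**If frequency means events per patient.** A mean is then a reasonable summary and 0 to 30.8% is not the matching interval, but a t interval still collapses at zero events. Assuming all ten patients are followed for 24 weeks, exposure is 10 × 24/52 = 4.6 patient-years. The exact Poisson upper limit for zero events is −ln(0.025)/4.6 = 3.689/4.6 = 0.80 events per patient-year.

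**The case against.** The strongest reply is that the plan never says the adverse event interval will be built from a mean and SD. It promises intervals without naming a method, and it assigns the t distribution only to differences between baseline and week 24. An exact interval would satisfy the text as it stands. That is right. A reader might infer that the plan itself produces a zero-width interval, and the documents do not support this.

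The drafting is also plainly loose. The same sentence puts demographic variables under the continuous heading, and those include sex and race. Elsewhere the protocol uses frequency for numbers of patients in response categories, and the enrolment-pause rule counts patients with a related serious event. The authors may well have meant patient counts. This too is fair, but it supports saying so: safety is a primary endpoint, and the intended measure and interval should not have to be guessed.

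Three further inferences should be resisted.

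- The planned summaries are not blind to clustering of events. One patient with ten events gives mean 1, median 0, SD 3.16; ten patients with one each give mean 1, median 1, SD 0.
- Exact limits are not always wider. At 1 of 10 the widths are 0.452 (t) and 0.443 (exact), and at 2 of 10 they are 0.603 and 0.531. Only the zero-event interval widens.
- Nothing says that extension-phase events will be pooled with weeks 0 to 24. The text is silent on the window.

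Finally, the study is small and descriptive, Section 15 admits its limited power, and no decision rule rests on an adverse event interval. That limits the consequence to how the safety result is reported and read.

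**Conclusion.** The point holds in a limited form. Section 15 and the synopsis misclassify adverse event frequencies as continuous, do not define them, and name no interval method for binary or count safety outcomes, while promising an interval for every estimate. Hypothesis A adds a before-and-after comparison and the pause rule counts patients, but neither supplies a method of estimation.

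The size is conditional. If the mean and SD label is carried into a t or Wald interval, the difference at 0 of 10 is between 0 to 0 and 0 to 30.8%. At 1 of 10 the t interval has an impossible lower limit. These figures assume a two-sided 95% level, all ten patients in the denominator, and frequency read as the proportion of patients with an event. The likelihood of the zero-event case rests on the assumed rates of 3% to 20%. The documents do not show that the sponsor would use the faulty interval, only that the plan does not rule it out. This is a wording fault worth correcting before analysis, not a flaw in the design.

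**What to change.** In Section 15 and the synopsis:

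1. Remove adverse events from the sentence on continuous variables.
2. State that, for serious adverse events and for infections, the number and percentage of dosed patients with at least one event in weeks 0 to 24 will be reported, with exact (Clopper-Pearson) two-sided 95% confidence intervals.
3. If event counts are also reported, give events per patient-year with exact Poisson limits, and show the extension phase separately. It is offered only to patients who improved, and it adds exposure that differs between patients.

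No change to data collection, visits or sample size is needed. The cost is slightly more analysis work and a wider, but informative, interval when no events occur.

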2.2 SECONDARY OBJECTIVES

Steroid-sparing benefit will be obtained. ***We hypothesize that we can reduce daily corticosteroid therapy by at least 20% in this population of treatment-refractory patients.***

To this end, a standardized corticosteroid tapering regimen will be utilized (Section 5). All subjects will remain on their initial prednisone dose until at least the first follow-up visit (week 6) and until they meet the definition of improvement and are rated as 'much improved' by both the physician and the patient or parent. The prednisone dose may then be reduced according to the standardized steroid tapering schedule in Section 5.

- a) To examine response to treatment in individual core set measures of disease activity as developed by IMACS, including Physician and Patient/Parent global activity, Muscle strength (by manual muscle testing, MMT-8), Physical function (by HAQ/CHAQ), Muscle enzymes, and Extra-muscular activity (by the Myositis Disease Activity Assessment Tool, MDAAT).
- b) To examine other core set activity measures as developed by PRINTO, including the Childhood Myositis Assessment Scale (CMAS), the Disease Activity Score (DAS) and Health Related Quality of Life Questionnaire (Childhood Health Questionnaire (CHQ-PF50) for children or SF-36 for adults.

- c) To examine improvement in patient reported outcomes, including health-related quality of life and fatigue measures, including the PROMIS fatigue questionnaire and PedsQL fatigue questionnaire. Both patient and parent questionnaires will be obtained, for patients < 18 years of age.
- d) (optional Assessment by Dermatology) To examine improvement in cutaneous activity, using the Cutaneous Dermatomyositis Area and Severity Index (CDASI) and the Dermatology Life Quality Index (DLQI), as well as periungual nailfold capillary density. To document changes in cutaneous findings by standardized photography.
- e) To examine improvement in muscle inflammation by examining a thigh/pelvis STIR MRI at baseline and 6 month follow-up.
- f) To examine that disease damage does not increase while under treatment with abatacept, by examining the Myositis Damage Index (MDI) at baseline and 6 month follow-up.
- g) To examine improvement of biomarkers that may relate to disease pathogenesis and the mechanism of action of abatacept in JDM, including:

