- h) To examine at baseline, 3 and 6 months biomarkers of disease including:
 - i. Immunophenotyping for CD4, CXCR3, IFN γ (TH1), CD4, CCR4, CRTH2, IL4 (TH2), CD4, CCR6, IL17a (TH17), CD4, CD25, Foxp3 (T regulatory cells), B cell markers and macrophage markers along with B71, B72, CTLA4, CT28 on fresh lymphocytes
 - ii. Isolation of T cells, B cells, dendritic cells, monocyte and macrophages, and freeze the isolated cells for subsequent molecular and functional analysis, including gene expression profiling
 - iii. Cytokine 30-plex panel on serum samples
 - iv. Peripheral blood mononuclear cells for RNA gene expression using a gene bead chip panel.

Biomarker studies will be blinded to the clinical assessment information and drug dose.

To evaluate immunogenicity and the pharmacokinetics of SC abatacept by the steady-state trough concentrations of abatacept at week 0, week 12 and week 24

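### One unadjusted p<0.05 threshold covers the 30-plex cytokine panel, the cell subsets and the gene chip, so false-positive biomarkers are likely

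*Combined protocol and SAP*

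**What the plan says.** Section 15.0 sets one significance rule: "For all statistical tests, a P-value of < 0.05 will be utilized to indicate statistical significance". The tests are also described generally: "Non-parametric Wilcoxon signed rank tests will be used to investigate changes in continuous variables". For the comparison of initial with week-24 values, the plan says these "and 24 weeks values will be analyzed by Student t distribution and Wilcoxon matched pair tests".

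The biomarkers are a secondary objective in Section 2.2 (item g): "To examine improvement of biomarkers that may relate to disease pathogenesis and the mechanism of action of abatacept in JDM, including". Section 3.1 lists them among the secondary endpoints and gives the sampling times: "To examine at baseline, 3 and 6 months biomarkers of disease including". Besides immunophenotyping, the list includes "Cytokine 30-plex panel on serum samples" and "Peripheral blood mononuclear cells for RNA gene expression using a gene bead chip panel". On sample size, Section 4.0 says: "The total number of subjects will be 10".

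The documents contain no Bonferroni, Holm or false-discovery-rate rule and no testing hierarchy. Nothing says that biomarker p-values are exploratory. Table 2 in Appendix E has a line for array data analysis and pathway analysis, but it sets no error rate.

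**The concern.** A 5% threshold per test is tolerable for a handful of clinical measures. Applied marker by marker to a panel of 30 cytokines, several cell subsets and a whole expression chip, it will usually produce significant results even if the drug does nothing to those markers.

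The biomarker objective is meant to inform on pathogenesis and mechanism of action, and Section 15 says the project may lead to a larger study. Spurious markers could be carried into that study. The trial is open label with a single arm, so no concurrent control group helps to screen them out. Blinding the biomarker laboratories to clinical data and drug dose (Section 3.1) does not address multiplicity.

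**Working it through.** The plan gives no power or family-wise error calculation to reproduce; 0.05 is a declared convention.

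**Inputs from the documents**
- Threshold 0.05 per test (Section 15). Sidedness is not stated; two-sided is assumed.
- 10 patients (Section 4.0) and 30 cytokines (Section 3.1).
- Named comparison: initial versus week 24 (Section 15). Biomarkers are also sampled at 3 months (Section 3.1), so a second comparison with baseline is possible.

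**Assumed:** 10,000 to 47,000 probes on the chip, because the documents give no count.

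**1. Cytokines, no true effects.** Expected false positives = m × 0.05. Chance of at least one, if independent = 1 − 0.95^m.
- Week 24 only, m = 30: 30 × 0.05 = 1.5; 1 − 0.95^30 = 0.785.
- Weeks 12 and 24, m = 60: 60 × 0.05 = 3; 1 − 0.95^60 = 0.954.
- The exact signed-rank test at n = 10 has true size 0.0488, which for m = 30 gives 1.46 and 0.777, almost the same.
- Correlation among cytokines changes the chance of at least one, usually downwards, but not the expected count.
- Calling a marker significant if either the t test or the Wilcoxon test passes raises the per-marker rate only to about 5.6% (simulation with normal data).

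**2. Chip, no true effects, per comparison.** 10,000 × 0.05 = 500; 20,000 × 0.05 = 1,000; 47,000 × 0.05 = 2,350.

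**3. Share of significant markers that are false.** With π the proportion of markers that truly change, the ratio of expected counts is (1 − π) × 0.05 / [(1 − π) × 0.05 + π × power]. Paired t-test power at n = 10 (noncentral t) is 14%, 29%, 62% and 80% for standardized changes of 0.3, 0.5, 0.8 and 1.0. The values of π and the effect sizes are assumptions.

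| π | Change (SD) | Calculation | False share |
|---|---|---|---|
| 50% | 0.5 | 0.025 / (0.025 + 0.1466) | 15% |
| 10% | 0.5 | 0.045 / (0.045 + 0.0293) | 61% |
| 1% | 0.8 | 0.0495 / (0.0495 + 0.0062) | 89% |

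The share exceeds half when π is below 0.05 / (0.05 + power): about 27%, 15%, 7.5% and 5.9% for the four effect sizes.

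**4. Which corrections are attainable.** The smallest two-sided exact signed-rank p-value at n = 10 is 2/2^10 = 0.00195.
- Bonferroni over 30 cytokines needs 0.05/30 = 0.00167, which the signed-rank test can never reach.
- Benjamini-Hochberg at 10% over 30 cytokines starts at 0.10/30 = 0.00333, so one cytokine at the minimum p-value can be declared. Over 60 tests it starts at 0.00167, and two are needed.
- On a 20,000-probe chip at 10% FDR, 0.00195 × 20,000 / 0.10 ≈ 391 probes would have to reach the minimum before any could be declared.

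**The case against.** The strongest reply is that Section 15 never names the biomarkers. Its list of what will be examined covers improvement criteria, core set measures, patient-reported outcomes, skin assessments and MRI. The array has its own line in Appendix E, so the authors may not have intended probe-by-probe testing at 0.05. On this view the biomarker analysis is merely unspecified. This stands in part: the rule reaches the biomarkers only through its general wording, and intent is uncertain. But the wording covers all tests, the markers are continuous secondary endpoints, and the Appendix E line supplies no alternative error rule. Anyone following the plan as written would use 0.05.

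Three stronger readings are tempting and are not supported.
- A reader might infer that 60 cytokine tests are planned. The only comparison Section 15 names is initial versus week 24, which is 30 tests; the week-12 comparison is an inference from the sampling times.
- A reader might infer that most significant biomarkers will be false. That depends on how many markers truly change and by how much, which the documents do not give. If the drug has a broad effect, most cytokine hits could be real.
- A reader might infer that the signed-rank floor rules out chip-level control under this plan. Section 15 also plans a Student t test, which has no such floor, and 391 of 20,000 probes is a high bar rather than an impossible one.

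The plan's warning of low power does not answer the point. It concerns missed effects, and low power raises the false share among results that do reach 0.05. It is fair to add that FDR control cannot separate a drug effect from background therapy or natural change in a single-arm study.

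**Conclusion.** The concern holds in this form: one unadjusted 0.05 threshold, through its general wording, governs high-dimensional secondary endpoints in 10 patients. With no true effects, about 1.5 false-positive cytokines are expected at week 24 (79% chance of at least one, assuming independence), or 3 (95%) if week 12 is also tested against baseline. On the chip, 500 to 2,350 are expected per comparison, resting entirely on the assumed probe count.

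That more than half of the significant markers are false is a possibility, not a finding. It is more plausible for a chip on which few genes change than for the cytokine panel. The primary 6-of-10 responder criterion has no planned test and is not affected, and no decision in the documents is tied to a biomarker p-value. The point should be corrected, but it does not threaten the trial's main conclusion.

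**What to change.** Add one paragraph to Section 15:
- Limit the unadjusted 0.05 rule to the clinical measures.
- For cytokines and cell subsets, apply Benjamini-Hochberg FDR control within each panel, for example at 10%, and state which comparisons (week 24 alone, or weeks 12 and 24) form the family.
- For the chip, apply FDR control with a t-based paired test, ordinary or moderated, because of the signed-rank floor.
- Name one test per panel in advance, rather than running both the t and Wilcoxon tests on the same change.
- Label any other biomarker p-values as descriptive.

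The FDR level is a choice; 10% suits the signed-rank test on 30 cytokines at n = 10. With only 9 complete pairs the smallest p-value is 0.0039, above the first step of 0.00333, so at least two cytokines would have to reach it.

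No extra patients, samples or visits are needed. The cost is fewer nominally significant biomarkers to report, and a moderated t-test may need software beyond the two packages that Section 15 names.
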